17.1. ADVERSE EVENTS

Adverse Events (AEs) will be coded using the MedDRA coding dictionary, Version 21.0.

Treatment emergent AEs (TEAEs) are defined as AEs that started or worsened in severity on or after the first dose of study drug. In section 5.0 of the protocol it states: 'the term study drug is used to refer to any blinded medication administered (i.e., any dosage of APT-1011 or placebo)'.

For further defining TEAEs below, study drug will also include single-blind (to subject) APT-1011 3.0 mg BID which histologic non-responders at Week 12 receive in Part 2.

TEAEs will be defined for each of the following periods:

- Part 1 of the study
- Part 2 of the study (with first dose of study drug being the first dose in Part 2)
- Parts 1 and 2 combined

For Parts 1 and 2 combined, histologic non-responders at Week 12 will be summarized for both their double-blind dosing in Part 1 and their single-blind (to subject) dosing in Part 2.

See Appendix 2 for handling of partial dates for AEs. In the case where it is not possible to define an AE as treatment emergent or not, the AE will be classified by the worst case; i.e. treatment emergent.

An overall summary of number of subjects and number of events within each of the categories described in the sub-

Author:

Version Number: 3.0

Version Date: 06NOV2019

Template No.: CS_TP_BS016 Revision 5 Reference: CS_WI_BS005

Page 49 of 70

section below, will be provided as specified in the templates.

Listings will include TEAEs and Non-TEAEs.

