#### 6.3.1.2 Recording and Reporting of Adverse Events

An AE must be promptly documented and recorded on the Adverse Events eCRF. The Investigator is responsible for recording all AEs observed or reported during the study, regardless of causality and/or clinical significance.

At each study visit, after the subject has had an opportunity to spontaneously mention any problems, the Investigator or designee should inquire about AEs by asking the appropriate open questions. In addition to straightforward subject observation (e.g., headache, nausea, etc.), AEs will also be documented from any data collected in the eCRF (e.g., laboratory values, physical examination findings, etc.) or other documents (e.g., subject diaries) that are relevant to subject safety.

The Adverse Event eCRF will record the following information.

- Name of the AE;
  - o Investigators should use correct medical terminology/concepts when recording AEs in the Adverse Event eCRF, avoiding colloquialisms and abbreviations.
  - Only 1 AE term should be recorded in the event field on the Adverse Event eCRF. If several conditions meet the criteria for AE reporting, each condition should be reported in the separate eCRF.
  - o If known, a diagnosis should be recorded on the Adverse Event eCRF rather than individual signs and symptoms (e.g., record only hepatic injury or hepatitis rather than jaundice and elevated transaminases). However, if a constellation of signs and/or symptoms cannot be medically characterized as a single diagnosis or syndrome at the time of reporting, each individual event should be separately recorded on the Adverse Event eCRF. If a diagnosis is subsequently established, all previously reported AEs based on signs and symptoms should be replaced by a single AE report based on the single diagnosis, with a starting date that corresponds to the starting date of the first symptom of the eventual diagnosis. Signs/symptoms of the reported AE should be described in the eCRF description field.
- Date of onset of the AE;
- Intensity (mild, moderate, or severe);
- Date of resolution (or statement that the event is ongoing);
- Action taken;
  - Concomitant medication or adjunctive therapy/procedure given will be recorded on the concomitant medication form or adjunctive therapy/procedure form of the eCRF, respectively.
- Subject outcome;
- Whether the event meets the definition of an SAE.

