APPENDIX 2. Partial Date Conventions

Imputed dates will NOT be presented in the listings.

ALGORITHM FOR TREATMENT EMERGENCE OF ADVERSE EVENTS:

START DATE	STOP DATE	ACTION
Known	Known, Partial or Missing	If start date < study drug start date, then not TEAE If start date >= study drug start date, then TEAE

Author:

Version Number: 3.0

Version Date: 06NOV2019

Template No.: CS_TP_BS016 Revision 5 Reference: CS_WI_BS005

Page 65 of 70

START DATE	STOP DATE	ACTION
Partial, but known components show that it cannot be on or after study drug start date	Known, Partial or Missing	Not TEAE
Partial, could be on or after study med start date	Known	If stop date < study drug start date, then not TEAE If stop date >= study drug start date, then TEAE
	Partial	Impute stop date as latest possible date (i.e. last day of month if day unknown or 31st December if day and month are unknown), then: If imputed stop date < study drug start date, then not TEAE If imputed stop date >= study drug start date, then TEAE
	Missing	Assumed TEAE
Missing	Known	If stop date < study drug start date, then not TEAE If stop date >= study drug start date, then TEAE
	Partial	Impute stop date as latest possible date (i.e. last day of month if day unknown or 31st December if day and month are unknown), then: If imputed stop date < study drug start date, then not TEAE If imputed stop date >= study drug start date, then TEAE
	Missing	Assumed TEAE

ALGORITHM FOR ASSIGNMENT OF TREATMENT EMERGENT ADVERSE EVENTS TO STUDY PARTS:

The rules below will be applied to AEs which were defined as TEAEs using the table above.

Author:

Version Number: 3.0

Version Date: 06NOV2019

Template No.: CS_TP_BS016 Revision 5 Reference: CS_WI_BS005

Page 66 of 70

START DATE	STOP DATE	ACTION
Known	Known,	If start date >= Part 2 study drug start date assign to Part 2
	Partial or	Otherwise:
	Missing	assign to Part 1
Partial	Known	If stop date < Part 2 study drug start date assign to Part 1
		Otherwise:
		If known components of start date are such that the start date
		is definitely >= Part 2 study drug start date, assign to Part 2
		or if known components of start date are such that the start
		date is definitely < Part 2 study drug start date, assign to Part
		1.
		Or if known components of start date are such that the start
		date might be >= Part 2 study drug start date, assign to Part 1
		and Part 2
	Partial	Impute stop date as latest possible date (i.e. last day of month

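### SAP 17.1 counts worsening adverse events as treatment-emergent, but neither Appendix 2 table tests for worsening, so some events are dropped or left out of the 3 mg BID summaries

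*SAP*

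**What the plan says.** SAP 17.1 gives two routes to treatment emergence. TEAEs are "defined as AEs that started or worsened in severity on or after the first dose" of study drug. The definition is applied to Part 1, to both parts combined, and to "Part 2 of the study (with first dose of study drug being the first dose in Part 2"). The single-blind 3 mg BID given to Week 12 non-responders counts as study drug here.

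Appendix 2 turns this into two tables.

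- **Emergence.** For a known start date: "If start date < study drug start date, then not TEAE". Where the start date is missing, or partial and possibly on or after first dose, a known stop date decides: "If stop date >= study drug start date, then TEAE".
- **Study part.** This table acts only on what the emergence table lets through: "The rules below will be applied to AEs which were defined as TEAEs using the table above". For a known start date: "If start date >= Part 2 study drug start date assign to Part 2", and otherwise Part 1.

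No row in either table mentions severity. SAP 17.1 has a worst-case default, but only "where it is not possible to define an AE as treatment emergent or not".

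Protocol 6.3.1 defines a TEAE by occurrence after first dose and is silent on worsening. The form fields in Protocol 6.3.1.2 include a date of onset, one "Intensity (mild, moderate, or severe") and a date of resolution. They include no date of severity change, and there is no instruction to open a new record when an event worsens.

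**The concern.** The definition and the algorithm give different answers for the same event, so the programmer has to choose between them.

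Events already open at Day 1 are plausible. AEs are collected from consent (Protocol 6.3.1.2.1), and screening and run-in last 4 weeks each.

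The switch at the end of Part 1 matters more. SAP 17 adds a pooled 3 mg BID column so that the safety of that regimen is fully described. SAP 3.3 drops the 3-day attribution rule because it could flatter the highest dose. Leaving post-switch worsening under the earlier assignment works against both aims.

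Protocol 6.3.1.2 can push onset dates earlier still. When separate signs are later gathered into one diagnosis, the single record takes the onset date of the first symptom. An event that became more severe after the switch may then carry a Part 1 or run-in date.

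**Working it through.** **Trace of the two rules** (known start date, one record per event):

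| Event | SAP 17.1 | Appendix 2 | Agree? |
|---|---|---|---|
| Starts before first dose, worsens in Part 1 | Part 1 TEAE | Not a TEAE | No |
| Starts before first dose, worsens after first Part 2 dose | Part 2 TEAE | Not a TEAE; never reaches the study-part table | No |
| Starts in Part 1, worsens after first Part 2 dose | TEAE in Part 1 and in Part 2 | Part 1 only | No |
| Starts in Part 2 | Part 2 TEAE | Part 2 TEAE | Yes |

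In the third row, SAP 17 places a switcher's Part 1 data in the randomized group and the Part 2 data in the single-blind group. The worsening is therefore absent from the single-blind column and from the pooled 3 mg BID column. For a responder who stays on the same dose, the arm is right and only the study part is wrong.

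**Partial or missing start dates.** If the start is missing or could fall on or after first dose, a stop date on or after first dose, or no stop date, makes the event a TEAE whether or not it worsened. Nothing is lost at the emergence step there. A partial date that can only precede first dose is treated as in the first two rows.

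**Scale.** Inputs are from Protocol 8.1.1: 20 subjects per arm; Week 12 response of 60% on 3 mg BID, 3 mg HS and 1.5 mg BID, 20% on 1.5 mg HS and 10% on placebo; no dropout before the switch.

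- Active responders: 3 × (20 × 0.60) + 20 × 0.20 = 36 + 4 = 40 of 80, which reproduces the protocol's figure.
- Placebo responders: 20 × 0.10 = 2.
- Non-responders: 8 (3 mg BID) + 8 (3 mg HS) + 8 (1.5 mg BID) + 16 (1.5 mg HS) + 18 (placebo) = 58.
- Of these, subjects who change dose: 58 − 8 = 50.
- Pooled 3 mg BID column in Part 2: 58 + 12 double-blind responders = 70.
- One missed subject: 1/58 = 1.7 points in the single-blind group, 1/70 = 1.4 points in the pooled column, 1/20 = 5 points in a Part 1 arm.

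The documents give no rate of worsening events, so the number affected cannot be calculated.

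**The case against.** The strongest reply is that nothing is miscounted if sites open a new record when an event worsens. The new start date then makes the existing rows give the SAP 17.1 answer. Protocol 7.1.2 promises a completion guideline, which is not among the documents, and SAP 17.1.1.1 foresees a subject reporting the same term more than once. This stands as a condition on the effect. It does not remove the inconsistency, because neither document requires a new record.

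Two other defences fail. Appendix 2 is titled for partial dates, but its emergence table opens with known start dates and the study-part table depends on that result. The worst-case default does not help, because a known start date always yields a definite classification.

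Some stronger readings are tempting, and the documents do not support them:

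- *Worsening events vanish.* An event that began in Part 1 is still a Part 1 TEAE; it is misattributed rather than lost. Events classed as not treatment-emergent remain in the listings (SAP 17.1).
- *Only the start date is ever used.* This is exact for known start dates. Some partial and all missing starts also draw on the stop date.
- *Safety at the highest dose must look better than it is.* The pre-dose error applies by the same rule to every arm, placebo included, and nothing suggests that it favours 3 mg BID. Only the post-switch error has a direction.
- *All 58 switch dose, at 5 points each.* Eight of them were already on 3 mg BID, and 5 points fits only a Part 1 arm of 20.

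It is also fair that the consequences are bounded. SAP 17 plans no between-group safety comparisons, and SAP 17.6 summarizes low cortisol and abnormal ACTH results directly from the measurements.

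**Conclusion.** The SAP contradicts itself: its stated definition includes worsening and its stated algorithm cannot detect it. Pre-dose events that worsen on treatment fall out of the TEAE tables in all arms. Part 1 events that worsen after the switch stay with the randomized group and are missing from 3 mg BID.

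The size per event is small, and the total is unknown. The conclusion rests on start dates being known and on worsening not being entered as a new record. The scale figures rest on the protocol's planning rates before dropout. No efficacy result is touched. The correction is still worth making, because the directional part of the error bears on the dose whose safety SAP 3.3 set out not to flatter.

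**What to change.** Add one row to each Appendix 2 adverse-event table: an AE with an earlier start date whose severity increased on or after the study drug start date (for Part 2, the Part 2 study drug start date) is a TEAE in the part where it worsened. Both tables need it, since the study-part table sees only events that pass the emergence table. Apply the rule wherever a new record or a worsening date was captured. Where neither exists, say so as a limitation in the safety summaries. If the rule cannot be supported, reconcile SAP 17.1 with Protocol 6.3.1 so that definition and algorithm agree, accepting that worsening is then not counted.

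The text change is two rows, plus reprogrammed emergence and study-part flags and rerun AE tables. A new eCRF note would help only from now on. Protocol 2.5 already reports interim results for Part 1, so past worsening without a date could be recovered only by querying sites.

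One dependency has to be settled at the same time. SAP 6.1 places the first Part 2 dose on the day after the Week 12 visit, while SAP 3.1 has the switch after Week 14. The two must be reconciled, because the new row is tested against that date.

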17.1.1. ALL TEAES

Incidence of TEAEs will be presented by System Organ Class (SOC) and Preferred Term (PT) and also broken down further by maximum severity and relationship to study drug.

17.1.1.1. Severity

Severity is classed as mild/ moderate/ severe (increasing severity). If a subject reports a TEAE more than once within that SOC/ PT, the AE with the worst case severity will be used in the corresponding severity summaries.

17.1.1.2. Relationship to Study Drug

Relationship for AEs, will be indicated by the Investigator as related or not related.

17.1.2. TEAES LEADING TO STUDY DRUG DISCONTINUATION AND STUDY WITHDRAWAL

TEAEs leading to permanent discontinuation of study drug and sudy withdrawal will be identified as those with an answer of yes to the question 'Did the AE cause the subject to discontinue from the study?' on the Adverse Events page of the eCRF.

For TEAEs leading to discontinuation, summaries of incidence rates (frequencies and percentages) by SOC and PT will be prepared.

17.1.3. SERIOUS ADVERSE EVENTS

Serious AEs (SAEs) are those events recorded as "Serious" on the *Adverse Events* page of the eCRF. A summary of serious TEAEs by SOC and PT will be prepared.

17.1.3.1. Relationship to Study Drug

Relationship for SAEs, will be indicated by the Investigator as related or not related. TESAEs with a missing relationship to study drug will be regarded as related to study drug in summaries.

Author:

Version Number: 3.0

Version Date: 06NOV2019

Template No.: CS_TP_BS016 Revision 5 Reference: CS_WI_BS005

17.1.4. ADVERSE EVENTS LEADING TO DEATH

TEAEs leading to Death are those events which are recorded as "Fatal" on the *Adverse Events* page of the eCRF. A summary of TEAEs leading to death by SOC and PT will be prepared.

17.1.5. ADVERSE EVENTS OF SPECIAL INTEREST

Adverse events of special interest include oral and esophageal candidiasis and symptoms of adrenal suppression or hypercorticism.

These will be identified from those ticked as yes to the question 'is this an AE of special interest?' on the Adverse Events page of the eCRF.

17.2. LABORATORY EVALUATIONS

Results from the central laboratory will be included in the safety reporting of this study for hematology, serum chemistry and urinalysis. Results will be provided by the central laboratory in SI units. IQVIA Biostatistics will not be performing any conversions to SI units.

A list of hematology, serum chemistry and urinalysis assessments to be included in safety outputs is included in the protocol, sections 6.3.2.1, 6.3.2.2 and 6.3.2.3.

The following summaries will be provided for laboratory data:

- Incidence of clinically significant out of range post-baseline values (for quantitative measurements and categorical measurements)
- Incidence of potential Hy's law (see section 17.2.2) at any time post-baseline.

17.2.1. LABORATORY SPECIFIC DERIVATIONS

Not applicable.

17.2.2. LABORATORY REFERENCE RANGES AND MARKEDLY ABNORMAL CRITERIA

Quantitative laboratory measurements will be compared with the central laboratory reference ranges in SI units and categorized as:

Author:

Version Number: 3.0

Version Date: 06NOV2019

Template No.: CS_TP_BS016 Revision 5 Reference: CS_WI_BS005

Page 51 of 70

- Low: Below the lower limit of the laboratory reference range.
- Normal: Within the laboratory reference range (upper and lower limit included).
- High: Above the upper limit of the laboratory reference range.

Values outside of the reference ranges and those determined to be clinically significant will be flagged as such in the data listings.

For qualitative and quantitative laboratory measurements, clinically significant values will be identified using the ALERT flag in the central laboratory data provided to IQVIA Biostatistics.

As per section 6.3.2.1 of the protocol, for this study potential Hy's law is defined as alanine transaminase (ALT) or asparate transaminase (AST) $\ge 3x$ ULN, and total bilirubin $\ge 2x$ ULN.

17.3. ECG EVALUATIONS

Results from the central Electrocardiogram (ECG) review will be included in the reporting of this study. The following ECG parameters will be listed for this study:

- PR Interval (msec)
- QRS Interval (msec)
- RR Interval (msec)
- QT Interval (msec)
- QTcF Interval (msec)
- QTcB Interval (msec)
- HR (bpm)
- Overall assessment of ECG (Investigator's judgment):
 - Normal
 - o Abnormal, Not Clinically Significant (ANCS)
 - o Abnormal, Clinically Significant (ACS)

The following summaries will be provided for ECG data:

- Incidence of markedly abnormal criteria at any time post-baseline
- Incidence of clinically significant abnormal ECGs at any time post-baseline

Author:

Version Number: 3.0

Version Date: 06NOV2019

Template No.: CS_TP_BS016 Revision 5 Reference: CS_WI_BS005

Page 52 of 70

17.3.1. ECG SPECIFIC DERIVATIONS

All the parameters listed in section 17.3 will be included in data provided by the ECG central reviewer, and will not be derived by IQVIA Biostatistics.

17.3.2. ECG MARKEDLY ABNORMAL CRITERIA

Markedly abnormal quantitative ECG measurements will be identified in accordance with the following predefined markedly abnormal criteria:

- Absolute values for QT interval, QTc interval, QTcB interval and QTcF will be classified as:
 - \circ > 450 msec
 - \circ > 480 msec
 - \circ > 500 msec
- Change from Baseline for QT interval, QTc interval, QTcB interval and QTcF will be classified as:
 - >30 msec increase from baseline
 - >60 msec increase from baseline
- Overall assessment of clinical significance (determined by investigator)

These markedly abnormal criteria will be programmed by IQVIA Biostatistics (with the exception of overall clinical significance).

17.4. VITAL SIGNS

The following Vital Signs measurements will be reported for this study:

- Systolic Blood Pressure (SBP) (mmHg)
- Diastolic Blood Pressure (DBP) (mmHg)
- Pulse Rate (bpm)
- Respiratory Rate (breaths/min)
- Temperature (°C)
- Weight (kg)

Author:

Version Number: 3.0

Version Date: 06NOV2019

Template No.: CS_TP_BS016 Revision 5 Reference: CS_WI_BS005

The following summaries will be provided for vital signs data:

- · Baseline and value by visit
- Incidence of markedly abnormal values at any time post-baseline
- Listing of subjects meeting markedly abnormal criteria.

17.4.1. VITAL SIGNS MARKEDLY ABNORMAL CRITERIA

Markedly abnormal quantitative Vital Signs measurements will be identified in accordance with the following predefined markedly abnormal criteria:

Variable	Unit	Low	High
SBP	mmHg	≤ 90 mmHg	≥ 180 mmHg
DBP	mmHg	≤ 50 mmHg	≥ 105 mmHg
Heart rate	bpm	≤ 50 bpm	≥ 120 bpm
Respiratory rate	resp/min	≤ 12 resp/min	≥ 25 resp/min
Body temperature	°C	≤35.6 °C	≥ 38.3 °C
Weight	Kg	≤ 45 kg	>= 120 kg

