6.4. RETESTS, UNSCHEDULED VISITS AND EARLY TERMINATION DATA

In general, for by-visit summaries, data recorded at the nominal visit will be presented. Unscheduled measurements will not be included in by-visit summaries, but will contribute to any summaries of clinically significant or markedly abnormal safety data 'at any time post-baseline'.

In the case of a retest (same visit number assigned), the earliest available measurement for that visit will be used for

Author:

Version Number: 3.0

Version Date: 06NOV2019

Template No.: CS_TP_BS016 Revision 5 Reference: CS_WI_BS005

Page 20 of 70

by-visit summaries.

Listings will include scheduled, unscheduled, retest and EOT visit data.

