6.7. COMMON CALCULATIONS

For quantitative measurements, change from baseline will be calculated as:

Test Value at Visit X – Baseline Value

For certain parameters percentage change from baseline will be calculated as

• 100 x (Test Value at Visit X – Baseline Value)/Baseline Value

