17.5. PHYSICAL EXAMINATION

Newly occurring clinically significant physical examination abnormalities will be captured and summarized as AEs. Physical examination data will be listed only.

Author: Version Number: 3.0

Version Date: 06NOV2019

Template No.: CS_TP_BS016 Revision 5 Reference: CS_WI_BS005

Page 54 of 70

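### SAP 17.4.1 flags weight only by absolute limits, so the markedly abnormal summary counts subjects who entered beyond a limit and does not register large weight gain below 120 kg

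*SAP*

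**What the plan says.** SAP 17.4 lists weight among the vital signs and plans three outputs: "Baseline and value by visit", "Incidence of markedly abnormal values at any time post-baseline", and a listing of subjects who meet the criteria. SAP 17.4.1 introduces its table with "Markedly abnormal quantitative Vital Signs measurements will be identified in accordance with the following predefined markedly abnormal criteria". The table has one low and one high limit per variable. For weight these are 45 kg or less and 120 kg or more. It has no change-from-baseline entry and no requirement that the baseline value lie inside the limits. Under SAP 6.4, unscheduled measurements "will contribute to any summaries of clinically significant or markedly abnormal safety data 'at any time post-baseline", so they can also trigger the flag.

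Two other parts of the SAP treat change directly. The ECG criteria in SAP 17.3.2 combine absolute limits with change limits, such as ">30 msec increase from baseline". SAP 6.7 supplies a formula: "For certain parameters percentage change from baseline will be calculated as". Section 17.4 does not apply it to weight.

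On the protocol side, Appendix 6 lists weight gain under hypercorticism. Section 8.9 says that clinically significant changes in clinical tests, vital signs among them, will be summarized. Sections 4.2.1 and 4.2.2 set no weight or BMI limit for entry.

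**The concern.** The study gives a corticosteroid for up to 52 weeks, and the weight effect that the protocol names is gain. A fixed limit measures where a subject stands, not how far the subject has moved. As a count of on-treatment events it therefore fails in both directions: it includes people who were beyond the limit before the first dose, and it leaves out people who gained a great deal but stayed under 120 kg.

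The layout in SAP 17 can repeat the first error. Under SAP 6.2, baseline for data other than adverse events is always relative to the first Part 1 dose. For Parts 1 and 2 combined, a Week 12 histologic non-responder appears in the randomized column for Part 1 data and in the single-blind 3 mg BID column for Part 2 data. A stable heavy non-responder can thus be counted in both.

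**Working it through.** The plan states no figure for this rule, so there is none to reproduce. The check applies the rule as written.

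**Inputs.** Flag if any post-baseline weight is ≤45 or ≥120 kg (SAP 17.4 and 17.4.1). Percent change = 100 × (value − baseline) / baseline (SAP 6.7). Arm size is 20, total 100 (protocol 8.1).

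**Step 1: example subjects.**

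| Baseline (kg) | Post-baseline (kg) | Change | Flagged? |
|---|---|---|---|
| 125 | 125 | 0% | yes |
| 125 | 121 | −3.2% | yes |
| 119 | 120.5 | +1.3% | yes |
| 44 | 44 | 0% | yes |
| 60 | 72 | +20% | no |
| 80 | 96 | +20% | no |
| 99 | 118.8 | +20% | no |
| 80 | 119 | 100 × 39/80 = +49% | no |

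**Step 2: gain needed to reach the high flag,** 120 − baseline:

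- from 60 kg: 60 kg (100%)
- from 70 kg: 50 kg (71%)
- from 80 kg: 40 kg (50%)
- from 90 kg: 30 kg (33%)
- from 100 kg: 20 kg (20%)

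Steps 1 and 2 use only the rule and need no weight distribution.

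**Step 3: scale.** The documents give no weight distribution. As an assumption, take weight as normal with mean 80 to 90 kg and SD 15 to 20 kg, with distribution function F.

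- Share outside the limits with no change at all, p = 1 − F(120) + F(45): 0.004 + 0.010 = 1.4% at 80/15, and 0.067 + 0.012 = 7.9% at 90/20. That is about 1 to 8 of 100 subjects.
- Chance of at least one such subject in an arm of 20, 1 − (1 − p)^20: 24% to 81%.
- If every subject inside the limits gained 20%, the share newly flagged high is [F(120) − F(100)] / [F(120) − F(45)]: about 9% to 26%.
- One subject in an arm of 20 is 1/20 = 5 percentage points.

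**Step 4: how many subjects could be counted in two columns.** Protocol 8.1.1 expects 40 of 80 active subjects to respond at Week 12 and 10% of 20 placebo subjects, which is 2. Non-responders are then 40 + 18 = 58 of 100, before dropout. Only those among them who are beyond a limit would be counted twice.

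**The case against.** The strongest reply is that the table does what it claims: it counts values outside stated limits, and it is not offered as a measure of weight gain. The steroid signal has its own routes. Protocol 6.3.4 requires attention to Appendix 6 symptoms at every visit and a cortisol-specific eCRF for such findings. SAP 17.1.5 says "Adverse events of special interest include oral and esophageal candidiasis and symptoms of adrenal suppression or hypercorticism", and SAP 17.5 says "Newly occurring clinically significant physical examination abnormalities will be captured and summarized as AEs". SAP 17.6 tabulates low cortisol or abnormal ACTH results and discontinuations for hypercorticism. Weights are also summarized by visit, and SAP Appendix 1 puts collected CRF variables in the listings. Weight is not a protocol safety endpoint (6.3.6), and protocol 6.3.3 places it in the physical examination, which is not a safety variable for analysis.

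Most of this stands. A reader might infer that steroid-type weight gain would go unseen in this trial; the routes above do not support that. A reader might also infer that a few heavy subjects will create a false dose pattern. That depends on an assumed weight distribution, and SAP 17 plans no statistical comparison of safety data, so it is a possibility and not a prediction.

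What remains is narrower. By-visit values do not count subjects who gained, adverse event reporting depends on the investigator's recognition, and SAP 17.4 names no subject-level summary of weight change. Having classed weight as a vital sign, the SAP gives it a criterion that does not address change, which is what protocol 8.9 asks for. The table shells are not available, so a baseline column there cannot be ruled out, but the prespecified criterion would still be absolute.

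**Conclusion.** The point holds for the markedly abnormal weight flag and the listing built on it. By the rule alone, a stable subject at or beyond a limit is counted as a post-baseline abnormality, and a gain of up to 49% from 80 kg (to 119 kg) is not. The number of subjects who would be flagged without any change, about 1 to 8 of 100, rests on the assumed weight distributions; the individual examples do not. No efficacy analysis, decision rule or protocol safety endpoint is affected. This is a low-cost improvement to one descriptive summary, not a defect in the trial's safety monitoring.

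**What to change.** Add to the weight row in SAP 17.4.1, or replace it with, a percent-change-from-baseline criterion for increase and one for decrease, using the SAP 6.7 formula. The sponsor should prespecify the threshold; 7% is only an example and has no source in the documents. At 7%, a subject starting at 80 kg would be flagged from 80 × 1.07 = 85.6 kg, and one stable at 125 kg would not. This follows the SAP's own ECG approach.

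For the absolute limits, keep all subjects in the count and show baseline status: already met at baseline, or newly met. Excluding those who met a limit at baseline would be worse, because a subject who enters beyond a limit and then deteriorates would drop out of the summary.

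The cost is an extra table row or column and a little programming. No new data are needed, since weight is part of the scheduled physical examinations. Subjects without a baseline weight leave the change denominator. They should be few, because the examination is scheduled at both Screening and randomization, and that denominator should be shown.
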